Current methods of video game adaptation often involve a change to the controller or game that reduces the amount of interaction the user has with the game [4]. These methods provide incomplete accessibility which can decrease the benefits of playing video games. For example, games that have been modified or designed with the intent to make the interaction simpler may result in less demands on strength, coordination, immersion, etc., meaning less benefits to be realized in these areas. The cost associated with adapting games or controllers may also be a barrier to their use. Adapted controllers also make it more difficult for users to play with others using a standard controller because controllers cannot be shared between players and the adaptive controller may have different requirements. Given that 70% of people who play video games play with others [6], the ability to participate with others is an incredibly important factor to participation.

Providing children with an upper limb amputation or difference with the ability to play any video game with a standard controller increase their ability to participate in a main-stream childhood experience. At RCC, we have developed a video game controller adapter that allows for one-handed play. It is easily attached and removed to a standard Xbox controller, which allows inclusive play between children with and without an upper limb amputation or difference. We propose that this new technology will increase both video game performance and satisfaction, allowing children with an upper limb amputation or limb difference to realize all of the benefits of playing video games with ease. We hope that this will ultimately improve quality of life for this population.

Research Purpose

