The aim of this research study is to explore whether a novel video game controller adapter designed at RCC can increase performance and/or user satisfaction while playing video games, in users with unilateral upper limb differences. This case series will use mixed quantitative and qualitative methods to compare performance and user satisfaction with and without the RCC designed video game controller adapter. We will assess performance using a standard Minecraft course for all participants. Satisfaction of the adapter will be assessed with a semi-structured interview and a Visual Analog Scale (VAS) for satisfaction, and the Quebec User Evaluation of Satisfaction with assistive Technology (QUEST) outcome measure to compare play with and without the adapter for each participant.

Research Methods

Participants & Sampling Technique: Participants will be selected through convenience sampling at the Rehabilitation Centre for Children in Winnipeg, Manitoba, to a sample size of 15-20. All participants will be between the ages of 7 and 17, with unilateral upper limb differences. The upper extremity limb difference will be from any cause (congenital, trauma, secondary to other medical complications), and of any level (partial hand, wrist disarticulation, transradial, elbow disarticulation, transhumeral, shoulder disarticulation). Participants will be able to communicate in English and have the cognitive ability to follow instructions. Participants will live in Winnipeg or be willing to travel to RCC for two in person appointments (initial evaluation and final evaluation). Participants will be included regardless of history of prosthesis use.

Appropriate participants will be identified by their treating clinician (MG) and informed of the study. If they are interested in participating, they will sign a consent to contact for research form, and be contacted by another member of the research team (EH), who is not involved in their clinical care to review the consent form and ask any questions. Participants may also be recruited through self identification by sharing study information through posters at RCC, the RCC website and social media.

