Data Collection: Each participant will provide informed consent before participating in any study related activities. At initial evaluation, each participant will complete a demographic questionnaire, as well as a semi-structured interview about their previous video game playing experiences, and their motivation to participate in playing video games in the future. The interviewing team member will record the interview on their phone and ensure that their phone is disconnected from the cloud. The recording will be transferred to the data storage system and then deleted from the phone. Anonymized data will be stored in a University of Manitoba Microsoft Teams environment. Following this interview, they will receive a training session from a team member (RG) on how to use the adapter and how to play Minecraft. This video game was chosen for its age appropriateness and need to use almost every button on the controller. Following the training, we will collect initial outcome measure data for both the with and without adapter conditions: time to complete the specified Minecraft “obstacle course”, accuracy of obstacle course (errors counted), VAS of satisfaction after playing, and the QUEST. Order of data collection with and without the device will be randomized to minimize a training effect.

Following the initial evaluation appointment, the participant will take home a tracking log, the video game controller adapter, and an Xbox with an Xbox One controller (if they do not already have one at home). Each participant will be asked to use the device daily and fill out the tracking log daily for 7 days. After which, each participant will return to RCC for the final evaluation appointment. At this time

the Minecraft “obstacle course” and evaluation will be repeated for gameplay with and without the adapter conditions. Finally, an exit semi-structured interview will be conducted to evaluate their experience with the adapter. Each participant will return the Xbox and controller if they were taken home. They will have the opportunity to keep the adapter if they wish.

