Data Analysis: The semi structured interviews will be analyzed using an inductive coding approach as described by Thomas [7]. A transcript of the audio recorded interview will be created, formatted, and analyzed for any initial impressions and general tone. Codes will be assigned to the content of the interviews and then codes will be grouped into categories based on similarity of intent. The categories will then be refined and revised as each interview is added as a data source. A paired t-test will be used to analyze the performance measures and QUEST responses in order to determine if there was a clinically important difference between playing with and without the adapter. A repeated measures ANOVA analysis will be used to evaluate the VAS satisfaction scores, in order to determine if there was an increase in satisfaction with increased use of the adapter.

[figure not shown]
Knowledge Translation

We plan to address knowledge translation in several ways through this study. On an organizational level, we hope to share the results with the rest of the Rehabilitation Centre for Children (RCC) and Specialized Services for Children and Youth (SSCY) partners by presenting them at the monthly learning series, Breakfast at SCCY. We hope the findings of this study may translate to help additional populations seen at SSCY centre (i.e., hemiplegia/Cerebral Palsy). We also plan to share the results and adapter design with the War Amps CHAMP program, so that other children with upper limb differences across the country may benefit from the adaptation. To share our results with other health care providers, we plan to submit our results to be presented at the Association of Children’s Prosthetic Orthotic Clinics (ACPOC), Orthotics Prosthetics Canada (OPC), and RESNA Annual Conferences. Finally, we plan to write an article for a peer reviewed open-access journal to support broader knowledge translation.

Research Team

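### The aim is to compare satisfaction with and without the adapter, but the only stated purpose of the VAS analysis is change with increased use

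*Protocol*

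**What the plan says.** The introductory text of the protocol states the hypothesis: "We propose that this new technology will increase both video game performance and satisfaction". Research Purpose turns this into an aim, to "compare performance and user satisfaction with and without the RCC designed video game controller adapter", and lists the instruments: "Satisfaction of the adapter will be assessed with a semi-structured interview and a Visual Analog Scale (VAS) for satisfaction", followed by the QUEST.

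Under Research Methods, Data Collection, the first visit gathers "initial outcome measure data for both the with and without adapter conditions", and the list of measures includes "VAS of satisfaction after playing, and the QUEST". After the home week, the "evaluation will be repeated for gameplay with and without the adapter conditions". Each child therefore gives four VAS scores: two conditions at each of two visits.

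Data Analysis attaches a purpose to each method. "A paired t-test will be used to analyze the performance measures and QUEST responses", and the sentence goes on to give the with/without difference as the reason. The VAS scores go to a repeated measures ANOVA whose one stated reason is "in order to determine if there was an increase in satisfaction with increased use of the adapter". The factors of that ANOVA are not named.

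**The concern.** The stated reason for the VAS analysis does not match the aim that the VAS is meant to serve. An analyst who follows Data Analysis as written has an instruction to look for growth in VAS satisfaction over the week of use, and none to compare the VAS between playing with and without the adapter.

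Two misreadings could follow if only the effect matching the stated purpose is reported. A benefit present from the first visit and unchanged at the second would not show on the VAS. And if that effect is the visit effect, a general gain from knowing the game better, equal in both conditions, could be reported as satisfaction growing with use of the adapter. If the condition effect is reported as well, neither problem arises.

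The missing factor names alone would not be a finding, because they can be left to a statistical analysis plan. The point is the purpose that the protocol does state.

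**Working it through.** The protocol gives no SD, effect size or significance level for the VAS, so there is no figure of its own to reproduce. The main step needs none of these.

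**Step 1: which contrast answers which question.** Let W1 and W2 be the mean VAS with the adapter at the first and second visit, and O1 and O2 the means without it.

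- Condition effect (the aim): (W1 + W2)/2 − (O1 + O2)/2
- Visit effect, conditions pooled: (W2 + O2)/2 − (W1 + O1)/2
- Change with the adapter only: W2 − W1
- Interaction (adapter-specific change): (W2 − O2) − (W1 − O1)

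The stated purpose matches one of the last three, not the first.

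**Step 2: two simple cases.**

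| True situation | Condition | Visit | With-adapter change | Interaction |
|---|---|---|---|---|
| Constant benefit D, no change over the week | D | 0 | 0 | 0 |
| Equal rise R in both conditions, no benefit | 0 | R | R | 0 |

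**Step 3: size, under assumptions.** Assumed: a 100 mm VAS, independent within-child residual SD s per score of 10 to 30 mm, and a two-sided 5% test. The sample size of 15–20 is the protocol's. Each contrast is tested with a one-sample t on n − 1 degrees of freedom; power comes from the noncentral t with noncentrality (true contrast) × √n / (contrast SD). The contrast SDs are:

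- condition and pooled visit: √(4 × s²/4) = s
- with-adapter change: √(2s²) = s√2
- interaction: √(4s²) = 2s
- condition, if the benefit varies between children with SD τ: √(s² + τ²)

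*Constant benefit of 15 mm, no growth.* Visit, with-adapter change and interaction are each significant in 5% of studies, the false-positive rate. Power of the condition effect, for n = 15 to n = 20:

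| s (mm) | τ = 0 | τ = 15 mm |
|---|---|---|
| 10 | >99% | 85–94% |
| 15 | 95–99% | 72–85% |
| 20 | 77–89% | 58–72% |
| 25 | 58–72% | 46–59% |
| 30 | 44–56% | 37–48% |

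For example, at s = 15 and n = 15 the noncentrality is 15 × √15 / 15 = 3.87, which gives 95%.

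*Equal rise of 10 mm in both conditions.* Chance of a significant result, for n = 15 to n = 20:

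| s (mm) | Visit effect | With-adapter change |
|---|---|---|
| 10 | 95–99% | 72–85% |
| 15 | 67–81% | 40–52% |
| 25 | 30–40% | 18–22% |
| 30 | 23–29% | 14–17% |

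The interaction stays at 5%.

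A simulation of 20,000 replicates with the 15 mm benefit and s = 15 agreed: condition 0.948 (n = 15) and 0.988 (n = 20), with visit, with-adapter change and interaction all between 0.048 and 0.052.

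**Step 4: what the choice of method implies.** With only two visits, a visit-only repeated measures ANOVA is the paired t-test: F equals t². Naming an ANOVA for the VAS when the paired t-test is named for the other measures suggests that more than two cells were in mind. A condition-by-visit model is therefore compatible with the text, but the text does not say so and does not assign its condition effect a role.

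**The case against.** The strongest reply is that this is a gap of emphasis. A clause giving one purpose does not exclude others. The aim, the collection of the VAS in both conditions, and the choice of an ANOVA over a paired t-test, read together, make condition the natural second factor; which effect is tested for which aim is ordinary content for a statistical analysis plan, which is not at hand. Satisfaction is also not left untested: QUEST has an explicit with/without test, the interviews address it, no outcome is primary, and using two satisfaction measures for different questions is legitimate. Finally, the power figures rest on SDs and effects that the protocol does not supply.

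Much of this stands. The condition-by-visit model is compatible with the text, the gap concerns the VAS only, and the closing words of the instrument sentence in Research Purpose, about comparing play with and without the adapter, may belong to QUEST alone, so nothing here relies on them. The millimetre figures are illustration.

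What does not stand is that nothing needs to change. Data Analysis gives the with/without purpose to two groups of outcomes and a different purpose to the third. That is a stated purpose at odds with the aim, not a detail left for later, and the QUEST test does not supply the missing VAS comparison.

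**Conclusion.** The concern holds. For a benefit that is equal at both visits, the effects matching the stated VAS purpose have expectation zero whatever the SD, so the VAS analysis as described could miss exactly the benefit that the protocol hypothesises. The percentages depend on the assumed scale, SDs and effects; the zero expectation does not.

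It should be fixed, but it is limited in reach: it affects one of several satisfaction measures in an exploratory case series, it bites only if the condition effect goes unreported, and no data are lost. A clarification before analysis is enough. Made then, it also prevents a choice among condition, visit and interaction after the results are seen.

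**What to change.** In Data Analysis, state that the VAS will be analysed in a within-child repeated measures or mixed model with condition (with/without) and visit (initial/final) as factors, and that the condition effect is the test of the with/without aim. Report the condition-by-visit interaction with its 95% confidence interval as an imprecise estimate of adapter-specific change with use, not as a decisive test.

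The cost is one or two sentences, no new data, and one added VAS comparison. The precision to expect, in units of the residual SD s, for n = 15 to n = 20 (half-width = t(0.975, n − 1) × contrast SD / √n):

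| Effect | 95% CI half-width | Detectable with 80% power | Same, at s = 15 mm |
|---|---|---|---|
| Condition | 0.55 to 0.47 s | 0.78 to 0.66 s | 12 to 10 mm |
| Interaction | 1.11 to 0.94 s | 1.56 to 1.32 s | 23 to 20 mm |

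The interaction may also be diluted if the home week improves play without the adapter. If half of a 15 mm gain carries over, it expects 15 − 7.5 = 7.5 mm, with power 27–36% at s = 10, 15–19% at s = 15 and 7–8% at s = 30. It cannot settle whether satisfaction grows with use, and the text should not promise that it will.
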